9.2.2 Expected Adverse Reactions

A list of possible safety events detailed in Section 9.1 includes most of the safety signals that could be associated with the study interventions. The study group will regularly review events capture to determine relationship to study interventions. In order to maximize patient safety we do plan to conduct a manual review of the initial 100 subjects enrolled in the study from each healthcare site. We will also review a minimum of 10 subjects from each participating healthcare system every quarter to monitor for adverse events and relatedness to study interventions.

9.2.3 Serious Adverse Events

Hospitalizations and deaths are serious events in this study. It should be noted that these adverse events classified as serious are already primary and secondary outcomes for this study (hospitalizations and deaths). Other serious events are those leading to incapacity and/or permanent disability and will also be captured as noted above.

9.2.4 Unanticipated Problems

The study team will remain vigilant for unanticipated problems. Trends of increasing frequency or rate of safety events in the intervention group will prompt review of individual cases by the study team and reporting to the oversight group (DSMB).

Other possible unanticipated problems including malfunctioning of the decision support system or non-adherence to recommended clinic protocols as well as possible mitigations are discussed in Section 13 Quality Control and Quality Assurance.

9.2.5 Procedures to be Followed in the Event of Abnormal Laboratory Test Values or Abnormal Clinical Findings

All participating subjects in the study including in both control group and intervention group will be under the direct care of primary care providers who will make final decisions on all interventions and direct patient care. Abnormal laboratory findings or clinical findings will be brought to the attention of the primary care provider according to the existing protocols in each healthcare system for appropriate clinical response.

9.3 Reporting Procedures

The study group will collect adverse events from all the participating healthcare systems and review at least monthly. There will be reports prepared for submission to the DSMB quarterly.

It should be noted that there will be some delay on the acquisition of data regarding some adverse events/outcomes. Hospitalizations which are not captured via the electronic health record but require reporting from the DFW Hospital Council may not be known by the study team for several months. Furthermore, information on other serious adverse events such as deaths may not be available to the study team until after review of the Social Security Death files.

9.4 Type and Duration of Follow-up of Subjects after Adverse Events

All study subjects in the intervention and control group will be followed according to best practices by their primary care providers in following established protocols in each healthcare system. As part of participation in the study, the intervention group will continue to be monitored by PIECES and practice facilitators during the 12 months of their participation in the study.

9.5 Halting Rules

The study can be halted at any time by the DSMB recommendations if there are concerns about patient safety, lack of enrollment or poor adherence to study plans and poor adherence to protocol.

9.6 Safety Oversight (DSMB)

The study has approval from the IRB at UT Southwestern which will oversee the study for Parkland Health and Hospital Systems and ProHealth of Connecticut. There is also IRB approval from the from the Texas Health Resources IRB and the North Texas VA IRB. NIDDK has constituted a DSMB that will review and approve final study protocol, address any major changes in protocol and have ultimate authority to halt the study according to the concerns detailed in Section 9.5.

10. Clinical Monitoring

10.1 Site Monitoring Plan

There will be several levels of monitoring in the study. Members of the study team will monitor the four healthcare systems to ensure compliance with human subject protection, study procedures, and interventions. There will be an initial site visit for each healthcare system for training and assurance of compliance. Practice facilitators at each site will report patient enrollment and intervention for eligible patients every three months. Pieces will monitor interventions provided to eligible patients and progress towards achievement of enrollment targets and implementation of interventions. In addition to capture of events from the EHR, the study team will review the records involving enrollment and adherence to protocol outcomes and safety events for the first 100 patients enrolled from each healthcare system as well as a minimum of 10 patients every 3 months. There will also be similar review of the first 10 patients enrolled from every participating study site (cluster) in each healthcare system. We will also verify the functionality of the clinical decision support system by reviewing a sample of patients enrolled in the study from each site every quarter.

11. Statistical Considerations

11.1 Study Hypothesis:

It is hypothesized that the PIECES-based interventions can reduce one-year (12 months) unplanned all-cause hospitalizations for patients with a triad of CKD, diabetes and hypertension.

Study Design:

A prospective stratified cluster randomization design will be employed. Patients are clustered by clinics, which are stratified by healthcare systems, and randomly allocated to either the PIECES-based intervention or a control (standard medical care) group using a randomized permutation block within each stratum. Based on assignment of his or her clinic, each patient will be assigned either to the Pieces group or a standard medical care group. Stratified randomization log will be created using SAS PROC PLAN with variable block sizes.

11.2 Sample size consideration:

We determined sample size based on the comparison of one-year unplanned all-cause hospitalization rates between the control and PIECES-based intervention groups.

The sample size formula developed by Donner [64] for stratified randomized trials was employed. From preliminary data we observe that the rate of unplanned all-cause hospitalization during the 1-year follow-up period is 14% across all four large health care systems in standard medical care group. We expect that the hospitalization rate in PIECES group will be 3% lower than that in the standard medical care group. Electronic health records show that the number of patients with coexistent CKD, hypertension and diabetes are 4,419, 4,738, 4,175 and 1,093 in Parkland, Texas Health Resources, ProHealth, and VA North Texas, respectively. The numbers of clinics are 25, 40, 50, and 9 in Parkland, Texas Health Resources, ProHealth, and VA North Texas, respectively. From a preliminary dataset extracted from

Parkland Healthcare System and THR Healthcare System, we obtained an intracluster correlation coefficient (ICC) of 0.015.

If we assumed ICC = 0.015 to detect a 3% difference in the rate of unplanned all-cause hospitalization, a total of 10,991 patients are needed to achieve 80% power at a two-sided 5% significance level. We would need to enroll 3,367, 3,610, 3,181, and 833 patients from Parkland, THR, ProHealth, and VA North Texas, respectively. Here, 10,991 patients are 76.2% of 14,425 patients from the 4 healthcare systems participating in the study. Waiver of consent has been obtained from all IRBs overseeing the study and no informed consent will be obtained from patients. There is an opt-out option available for patients in the implementation and in the control groups and based on the nature of the interventions a small number of opt-out requests is expected. Additional practice sites/ clinics will be available at 3 of the 4 participating health care systems as enrollment sites for additional patients if required in the future.

11.3 Statistical Analysis Plan:

Standard descriptive analysis will be performed where we summarize continuous variables by mean and standard deviation, and categorical variables by count and percentage. The one-year unplanned all-cause hospitalization rates will be compared using the generalized Mantel-Haenszel procedure as presented by Donner [64], which is suitably adjusted for clustering. Furthermore, we will use generalized linear mixed model (GLMM) to examine if there is a significant difference in hospitalization rates between two intervention groups after controlling for potential confounding patient, clinician and clinic factors. The mixed model includes clinic random effects to account for within-cluster correlation. Univariate mixed models will be employed to assess the marginal association between the outcome and individual covariates. The final multivariate model will include covariates identified by the stepwise variable selection procedure as well as those considered to be clinically important *a priori*. Similar analysis will be performed to compare the rates of disease-specific hospitalization. As secondary analyses, the Kaplan-Meier plots will be generated to explore the difference in time to hospitalization between the two arms. Cox models with frailty will be implemented to evaluate the treatment effect on the event times of hospitalization, CV, and death events, controlling for confounding factors. Random effects for clinics are also included. Similar strategy of univariate and stepwise variable selection procedure in mixed model will be implemented to the Cox models with frailty. Statistical significance will be reported for $p\text{-value} < 0.05$. All statistical analyses are performed using statistical software SAS 9.4 (SAS Institute, NC, Gary).

To construct and evaluate predictive models for unplanned all-cause hospitalizations, disease-specific hospitalizations, 30-day readmissions, cardiovascular events and deaths, the total cohort will be randomly separated into derivation and validation datasets (2/3 and 1/3 sample, respectively). Based on the derivation set, we will select independent variables with $p\text{-value} < 0.20$ from univariate analysis as candidate variables for multivariate analysis. We will explore possible contributions to models from interactions of independent variables and from splines, transformations, and recursive partitioning for continuous variables. We will use the stepwise variable selection procedure on generalized linear mixed model (GLMM) to identify variables that are significantly associated with outcome variables such as hospitalization, 30 day readmissions, cardiovascular events and deaths. The goodness of fit criteria and the Bayes Information Criterion (BIC) will be used for model selection.

The resulting model will be externally validated based on the validation dataset. We will evaluate calibration through the Hosmer-Lemeshow test; we will measure discrimination by the

c-statistic, the area under the curve (AUC) for the receiver operating characteristic (ROC) curve and by the range of predicted risks. We will divide the patients into five groups based on the quintiles of their predicted risk by the model. We will compare the true event rate among the quintile groups to examine how well the predictive model separate patients at different levels of risk.

12. Source Documents and Access to Source Data/Documents

The main source of data will be through Pieces extraction of patient data from the EHRs of all study sites. Only the PI and study team members who are HIPAA certified will have access to this data. The data will be de-identified before transfer to the statistical team for analysis. Other sources of data is readmission data from the DFW Hospital Council, Pro Health databases and VA of North Texas databases/information.

13. Quality Control and Quality Assurance

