The study will employ a prospective stratified cluster randomization design. The stratum is each of the four large healthcare systems participating in the study. The unit of randomization will be primary care practices. In some healthcare systems (Parkland and North Texas VA) primary care practices are defined by an individual primary care practitioner caring for a unique group of patients with a permanently designated team of one RN and one medical assistant with no overlap with the practices of other primary care practitioners. In other healthcare systems (THR and ProHealth) clinical practices are defined as group of patients cared by practitioners sharing personnel and workflows in the same physical location and randomized as a single unit. The cluster design of the study is best suited to detect important differences in outcomes between the intervention and control groups^[8,55]. The decision to use primary care practices as a unit for randomization in the study is based on the ability to implement different models of care in the active intervention sites as compared to the control sites. The collaborative model of care which includes novel information technology, subject identification, facilitation of patient care, monitoring of outcomes and participation from facilitators can be most efficiently applied to the workflow of practices when they are fully randomized to active intervention. The cluster randomization design with practices receiving collaborative primary care-subspecialty care versus standard care also limits the risk of cross-contamination between intervention and control groups in the study.

Primary care practices will be stratified by healthcare systems and randomly allocated to either intervention group or standard medical care group using a randomized permutation block within stratum. Based on the assignment of the practice where a patient receives medical care each patient will be assigned either to the intervention group or the standard medical care group.

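### The adjusted GLMM and frailty Cox models do not commit to the healthcare-system strata, so their standard errors may be too large

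*Combined protocol and SAP*

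**What the plan says.** Section 4 sets the design: "Primary care practices will be stratified by healthcare systems and randomly allocated to either intervention group or standard medical care group", using permuted blocks within stratum. Sections 5.4 and 11.1 repeat this, and section 11.2 sizes the trial with a formula for stratified cluster trials.

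Section 11.3 then describes the treatment-effect analyses.

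- **Main comparison.** "The one-year unplanned all-cause hospitalization rates will be compared using the generalized Mantel-Haenszel procedure", adjusted for clustering and taken from the paper on stratified cluster designs cited as reference 64.
- **Adjusted GLMM.** This compares the arms "after controlling for potential confounding patient, clinician and clinic factors". On structure: "The mixed model includes clinic random effects to account for within-cluster correlation". On what is adjusted for: "The final multivariate model will include covariates identified by the stepwise variable selection procedure as well as those considered to be clinically important". That importance is to be judged in advance, but the a priori set is not listed.
- **Cox models with frailty**, for hospitalisation, CV events and death. On clustering: "Random effects for clinics are also included". On the choice of covariates the plan adds: "Similar strategy of univariate and stepwise variable selection procedure in mixed model will be implemented to the Cox models with frailty".

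Healthcare system is not named in the GLMM or the Cox models as a fixed effect, a random effect or a stratification factor. In the Cox text, the statement that clinic random effects are added on top of a frailty term also leaves the level of the frailty unclear.

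**The concern.** Stratified randomisation balances the systems across arms, so differences between systems do not add to the sampling variance of the treatment contrast. A model whose only structure is a clinic random effect does not know this. It counts between-system differences as clinic variance and charges them to the treatment effect, so the reported standard error exceeds the true one.

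The documents give reasons why recorded rates may differ. Section 5 describes a safety-net system, a private network, a veterans' system and a Connecticut physician network. Sections 3.2.1 and 15.1 describe different routes for capturing hospitalisations, with regional matching for the VA still only being explored.

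At stake are the adjusted hospitalisation result and the secondary time-to-event results, which may carry wider intervals and larger p-values than the design justifies. Whether they do depends on a modelling choice that the plan leaves open.

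**Working it through.** **The plan's own figure.** For 14% versus 11%, two-sided 5% and 80% power, the simple sample size is 1,907 per arm. With ICC 0.015 and section 11.2's record counts per practice (4,419/25, 4,738/40, 4,175/50, 1,093/9), the design effects 1 + (m − 1) × 0.015 are 3.636, 2.762, 2.237 and 2.807. Their patient-weighted mean is 2.881. Then 2 × 1,907 × 2.881 ≈ 10,990, against the stated 10,991. So N reproduces with one common rate.

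**Inputs to the check.** From section 11.2: 25/40/50/9 practices (124 in all), 3,367/3,610/3,181/833 patients to enrol, ICC 0.015, pooled control rate 14%, difference 3 points. Assumed: control rates by system, since only the pooled figure is given, and 1:1 allocation.

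**Closed form.** SE ratio (without/with system) = √(1 + B/W). B is the between-system variance of the rates, weighted by practices. W is the average of p(1 − p)[ICC + (1 − ICC)/m] over practices, with m = enrolled patients per practice (134.7, 90.3, 63.6, 92.6).

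- 16/13/12/18%: mean 13.56%, √B = 1.93 points, √W = 5.59 points. Ratio = √(1 + 1.93²/5.59²) = 1.058.
- 18/12/11/20%: mean 13.39%, √B = 3.22, √W = 5.52. Ratio = √(1 + 3.22²/5.52²) = 1.158.
- Equal rates: B = 0, ratio 1.

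**Simulation, logistic GLMM** (4,000 trials per setting, beta-binomial practices, no other covariates):

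| Assumed rates | Mean SE with / without system | Size with / without | Power with / without |
|---|---|---|---|
| Equal | – | 4.9% / 4.8% | 88.4% / 88.3% |
| 16/13/12/18% | 0.0905 / 0.0953 | 5.4% / 4.2% | 88.9% / 86.2% |
| 18/12/11/20% | 0.0915 / 0.1063 | 5.1% / 2.3% | 89.2% / 81.1% |

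The SE ratios are 0.0953/0.0905 = 1.05 and 0.1063/0.0915 = 1.16, as the closed form predicts. Without system the actual SD of the estimate is 0.0894 and 0.0917, so the reported SE is too large by 7% and 16%. With system, SE and SD agree within about 1%. Mean null log odds ratios lie between −0.0022 and 0.0017 in all settings, so there is no bias.

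**Variations.** With unequal practice sizes (CV 0.6, assumed), power is 85.6% versus 82.5% and 87.0% versus 77.2%. If the ICC of 0.015, which came from Parkland and THR, already contains their difference, it is 90.5% versus 87.8% and 95.5% versus 88.6%. A separate simulation with other assumed rates gives SE ratios of 1.01 (equal), 1.04 (16/13/13/15%) and 1.11 to 1.12 (18/12/12/16%). Its stress case of 20/12/9/20% gives about 1.30, with power 70% against 86%.

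**Simulation, Cox with clinic frailty, time to hospitalisation** (2,000 trials, stratified by system versus not). Power is 87.4% versus 87.1%, 87.6% versus 84.6%, and 90.3% versus 82.6% for the three tabulated rate sets. SE ratios are 0.998, 1.052 and 1.159. At each test's own empirical 5% critical value, power in the two unequal settings is 86.8% versus 86.3% and 91.3% versus 90.6%. The loss therefore comes from the overstated SE and not from a noisier estimate.

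**Rarer events.** The same closed form and relative spreads, with assumed overall rates of 3 to 5%, give an SE excess of about 1 to 2% (first unequal pattern) and 3 to 5% (second).

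**If system is a stepwise candidate** (retention at p < 0.05, assumed), it is kept in 91% and 100% of trials in the unequal settings. Power returns to 88.8% and 89.2%.

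**The case against.** The strongest reply is that the text does not exclude system. It is an obvious clinic-level factor, and the selection step would usually keep it where it matters most. That stands: the documents support saying that system is not guaranteed, and a reader who infers that it will be left out goes further than they do. What remains is that the result turns on an unstated choice of candidates, with no entry or retention threshold given for these models.

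Three further replies also stand. The rates by system are assumptions, and under the plan's single 14% the loss is nil. The simulated models carry no patient or clinician covariates, and any covariate that explains differences between systems would shrink the excess, so the figures lean towards a worst case. The hospitalisation figures cannot be carried over to CV events and death, where the excess is probably small.

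A reader might also infer that the trial is underpowered, that its main test ignores the stratification, or that false positives rise. None of these follows. The main comparison and the sample size rest on methods for stratified cluster designs, and the error in the supportive models is conservative. Nor does this check give grounds for replacing stepwise selection with a fixed covariate list.

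**Conclusion.** The point holds as a gap in pre-specification of the adjusted GLMM and the secondary frailty Cox models. If system is omitted and rates differ between systems, the reported SE is too large. For hospitalisation the excess is about 0%, 6% and 16% under the three main sets of assumed rates. The power loss runs from nil to roughly 8 to 10 points without other covariates; the upper end needs the 11 to 20% spread and, for the full 10 points, unequal practice sizes. For CV events and death the excess is about 1 to 5% at assumed rates of 3 to 5%. All of it vanishes if rates are equal or if system is offered to selection and kept. The effect estimate is unbiased and type I error is not inflated. The Mantel-Haenszel comparison and N = 10,991 are untouched. The mechanism is certain; the size is not, because the documents give no rates by system.

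**What to change.** Add to section 11.3: every treatment-effect GLMM includes healthcare system (four levels) as a fixed effect, and every frailty Cox model is stratified by healthcare system with a clinic-level frailty, regardless of variable selection. This also settles the level of the frailty term.

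The change is a free improvement. It uses three degrees of freedom among 124 practices in the GLMM and costs no power when system rates are equal (88.4% with system, 88.3% without). It needs no new data and leaves the sample size and the Mantel-Haenszel comparison as they are. The only administrative step is the IRB submission that section 14.2 requires for any protocol change. It should be made before outcomes are analysed, so that including system cannot look data-driven.

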7.3 Follow up Visits

Measures of blood pressure, blood glucose, kidney function (creatinine, eGFR), lipid levels, urine protein/urine albumin as well as pre-specified safety events will be captured from electronic health records at the time of patient contacts with the healthcare system for scheduled or unexpected visits for patients. Information will be then directed to primary care teams per study protocol.

Main study outcomes will be captured throughout the study for both intervention and control groups using the same tools in the electronic health record and access to DFW Regional Hospital Council, ProHealth database and VA electronic information systems.

The study does not specify the frequency of visits for study participants. It is anticipated that patients with the triad of CKD, diabetes and hypertension will usually be seen at a minimum of every 3-6months in most participating clinics.

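### The adjusted GLMM and Cox treatment-effect models pick covariates by stepwise selection from a pool not limited to baseline, so the adjusted effect may be biased and its 5% error rate is not guaranteed; the Mantel-Haenszel comparison is unaffected

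*Combined protocol and SAP*

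**What the plan says.** Section 11.3 first compares one-year unplanned all-cause hospitalisation rates between arms with a generalized Mantel-Haenszel procedure adjusted for clustering. It then adds a GLMM with clinic random effects, to test the difference between arms "after controlling for potential confounding patient, clinician and clinic factors". Each covariate is first examined in a univariate mixed model, and then: "The final multivariate model will include covariates identified by the stepwise variable selection procedure as well as those considered to be clinically important" a priori. A similar analysis is planned for disease-specific hospitalisation. For time to hospitalisation, cardiovascular events and death: "Similar strategy of univariate and stepwise variable selection procedure in mixed model will be implemented to the Cox models with frailty".

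The section gives no covariate list, no entry or stay threshold for these models, and no time limit on covariate values. The p<0.20 screen later in 11.3 belongs to the predictive models only. The section does not say whether treatment is forced into the model, or which result decides if the Mantel-Haenszel test and the GLMM disagree.

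On the data available, Section 7.3 says: "Measures of blood pressure, blood glucose, kidney function (creatinine, eGFR), lipid levels, urine protein/urine albumin as well as pre-specified safety events will be captured" at patient contacts during follow-up. Table 7.1 lists laboratories and medication review at every visit, and Section 8.2 includes haemoglobin A1C among the laboratories.

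**The concern.** Two separate problems follow from this rule.

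The first is over-adjustment. Section 6.5 names blood pressure control, ACEI/ARB use, statin use and A1C as targets of the intervention. Follow-up values of these variables are in the data, and a rule driven by association with the outcome may select them. Conditioning on a variable that treatment has changed removes whatever effect runs through it. It can also create a difference where there is none, if the variable is associated with hospitalisation for other reasons, such as adherence.

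The second is selection itself. The pool includes clinician and clinic factors, and there are only 124 practices (25 + 40 + 50 + 9). Choosing practice-level covariates because they explain between-practice variation in these same data makes the remaining variation look too small. The p-value is then read as if the model had been fixed in advance.

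At stake are the adjusted hospitalisation results and, more seriously, the cardiovascular-event and death results, for which 11.3 names no treatment comparison other than the Cox models.

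**Working it through.** **1. The plan's sample size.** Section 11.2 gives these inputs: "the rate of unplanned all-cause hospitalization during the 1-year follow-up period is 14% across all four large health care systems"; "We expect that the hospitalization rate in PIECES group will be 3% lower than that in the standard medical care group"; "we obtained an intracluster correlation coefficient (ICC) of 0.015"; and "a total of 10,991 patients are needed to achieve 80% power at a two-sided 5% significance level". Equal allocation is assumed, since no ratio is stated.

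- Two proportions, 14% against 11%, pooled variance: n per arm = [1.96·√(2·0.125·0.875) + 0.8416·√(0.14·0.86 + 0.11·0.89)]² / 0.03² = 1,907.
- Design effect per stratum, 1 + (m − 1)·0.015, with m = available patients / clinics = 176.8, 118.5, 83.5, 121.4: 3.64, 2.76, 2.24, 2.81. The patient-weighted mean is 2.88.
- Total: 2 × 1,907 × 2.88 (unrounded mean) = 10,990, against 10,991 stated.

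The figure reproduces. It is built for an unadjusted stratified cluster comparison, and it cites the same source as the Mantel-Haenszel test.

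**2. Standard error with the patients to be enrolled.** Effective sample size = Σ n/[1 + (n/k − 1)·0.015] over 3,367/25, 3,610/40, 3,181/50 and 833/9 = about 4,655.

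- No effect: SE = √(4·0.14·0.86/4,655) = 1.02 points.
- 14% against 11%: SE = √(2·(0.1204 + 0.0979)/4,655) = 0.97 points, so power = Φ(3/0.968 − 1.96) = 87%. This exceeds 80% because the enrolled clusters are smaller than the available ones used in step 1.

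**3. Adjusting for one post-baseline covariate.** Suppose the intervention shifts the covariate by a, and the covariate is associated with hospitalisation by g. The adjusted effect then moves by a·g. The values of a are the changes in the pilot table of Section 2.2.3, which are uncontrolled before-after changes in 107 patients. The range for g, 1 to 5 points, is an assumption. With no true effect, the rejection rate is Φ(−1.96 + ag/1.02) + Φ(−1.96 − ag/1.02). With a true 3-point effect of which a·g is removed, power is Φ((3 − ag)/0.968 − 1.96).

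| Covariate (pilot change) | a, points | a·g, points | Rejection with no effect | Power (87% unadjusted) |
|---|---|---|---|---|
| Systolic BP at goal, 34.8% to 44.0% | 9.2 | 0.09 to 0.46 | 5.1% to 7.4% | 85.1% to 74.6% |
| ACEI/ARB, 57.8% to 87.2% | 29.4 | 0.29 to 1.47 | 6.0% to 30.4% | 79.8% to 35.2% |
| Statin, 45.0% to 79.8% | 34.8 | 0.35 to 1.74 | 6.4% to 40.2% | 78.2% to 25.5% |

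**4. Selection among baseline covariates only.** Simulation with no treatment effect: 124 clinics, enrolled sizes, 14% rate, ICC 0.015, a linear random-effects model, treatment and stratum forced in, forward-backward stepwise selection, 2,500 runs per row (Monte Carlo SE about 0.45 points). Five patient-level candidates were prognostic; all clinic-level candidates were irrelevant.

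| Candidates | Threshold | Unadjusted | Stepwise | Pre-specified list |
|---|---|---|---|---|
| 15 patient | 0.05 | 5.6% | 5.6% | 5.5% |
| 15 patient, 10 clinic | 0.05 | 5.2% | 6.1% | 5.7% |
| 15 patient, 10 clinic | 0.20 | 4.4% | 5.3% | 4.5% |
| 10 patient, 30 clinic | 0.20 | 5.8% | 8.5% | 5.9% |

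In the last row an average of 5.6 irrelevant clinic-level variables entered the model. A second, simpler simulation (practice-level linear model, 8,000 runs, 10 to 30 irrelevant practice-level candidates, entry at 0.05 to 0.15) gave 5.3% to 7.8%.

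The linear model stands in for the GLMM. The univariate screen and the Cox models were not simulated.

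**The case against.** The primary comparison does not depend on any of this. Section 11.3 puts the Mantel-Haenszel test first, the sample size is built for that kind of comparison, and it selects no covariates. That stands, and it limits the point to the adjusted analyses. It gives no cover to cardiovascular events and death.

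Over-adjustment is inferred. The plan speaks of confounding factors, and a confounder in the ordinary sense is not a consequence of treatment; Section 7.3 describes data capture, not the covariate pool. This is fair: the documents permit follow-up values to enter but do not say that they will. The point is the missing restriction.

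Two stronger readings are tempting. A reader might infer that the error rate of the adjusted models exceeds 5%. The documents do not support this: no threshold or number of candidates is given, and with patient-level baseline candidates the simulated error equalled the unadjusted one. The two middle rows differ from unadjusted by about 0.9 points, too little to settle with this number of runs. A reader might also infer that the trial's 80% power collapses. From z = 2.80, losing a quarter of the effect leaves Φ(2.10 − 1.96) = 56%, and losing half leaves Φ(1.40 − 1.96) = 29%. But no passage supports either share, and the 80% belongs to the unaffected test.

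Finally, different covariates for different outcomes are not an error, provided that each set is fixed in advance.

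**Conclusion.** The concern holds for the GLMM (all-cause and disease-specific hospitalisation) and for the Cox frailty models (hospitalisation, cardiovascular events, death). Their covariates are chosen on the outcome from an unlisted pool with no baseline limit. The adjusted effect may therefore be biased by variables that the intervention targets, and its type I error is not guaranteed at 5%.

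The size depends on choices that the plan leaves open. Selection among patient-level baseline covariates costs nothing detectable. A clear excess needs many clinic-level candidates with a loose threshold. Selection of a post-baseline target can matter more, but every figure for it rests on the assumed association g and on an uncontrolled pilot, and is illustrative only. The primary Mantel-Haenszel result is sound on this point. The change should be made because it is cheap and because the cardiovascular-event and death results have no other named analysis.

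**What to change.** In Section 11.3, for every treatment-effect model:

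- Replace the univariate screen and stepwise rule with a covariate list fixed before the interim efficacy analysis at 50% of the primary outcome data (Section 4). The list may differ by outcome if each is fixed by then. Possible entries are age, sex, baseline eGFR, unplanned hospitalisation in the prior year, cardiovascular history and practice size.
- Force in treatment and healthcare system, the randomisation stratum.
- Take practice and clinician factors from before the practice's randomisation, and patient factors from before that patient's enrolment or index visit. Patients enrol over two years, so patient values cannot all predate practice randomisation. Define the index date in the same way in both arms.
- State that no later variable may enter.
- State that the Mantel-Haenszel test decides the primary outcome and that the GLMM is supportive.
- Keep stepwise selection for the predictive models only.

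In the simulation a pre-specified list held the error at 4.5% to 5.9%, against 4.4% to 5.8% unadjusted. The cost is SAP wording, with no additional patients or visits. The team should check that prior hospitalisations outside each system can be obtained, since these come from regional, ACO and VA sources (Sections 3.2.1 and 15.1). The downside is small: the list must be agreed early and cannot adapt to unexpected predictors.
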